C8.d. Inclusion/Exclusion criteria (Table 5). Patients on PAH therapy will be enrolled provided they have had no new PAH therapies introduced for 12 weeks (see Table 5 for specifics). We will include premenopausal women but will track menstrual cycle dates and measure sex hormones at each visit; physiologic variations should be balanced by the cross-over design (i.e., at least four to five menstrual cycles per 18 week treatment assignment). At least four weeks of clinical stability (no hospitalizations or titration of PAH therapies) will be required prior to randomization. Additional exclusion criteria speak to the elimination of other types of PH (#2, 5-6) or conditions in which DHEA is untested (#7-8) or has uncertain or potentially harmful effects (#1, 9-11). Indwelling (>3 months) levonorgestrel IUDs will be allowed. The progestin effect of hormone-releasing IUDs occurs primarily at the endometrium¹⁴⁷. Serum hormone levels can be affected transiently (out to seven days postinsertion) but there is gradual decline over time which stabilizes. In a potential female subject with a long-term (3 months-5 years) hormone-containing IUD in place, systemic progestin levels are stable and, especially given the cross-over design, should not confound results.

Table 5. Inclusion and Exclusion Criteria

Inclusion Criteria

- mPAP \geq 25 mmHg at rest, pulmonary capillary wedge pressure or left ventricular end-diastolic pressure \leq 15 mmHg, and PVR > 3 Wood units at any time prior to study entry.
- Diagnosis of PAH that is 1) idiopathic, 2) heritable or 3) associated with connective tissue disease, congenital systemic-to-pulmonary shunt, porto-pulmonary hypertension, drug or toxin use
- Pulmonary function testing documenting forced expiratory volume in one second/forced vital capacity ratio \geq 70% predicted, total lung capacity \geq 70% predicted.
 - If TLC is mildly reduced (60% $<$ TLC% $<$ 70%), computerized tomography (HRCT or non-HRCT) documenting no significant interstitial lung disease may be used to fulfill this requirement.
- Chest tomography documenting no more than moderate parenchymal lung disease with clinician designated WHO I PAH and meeting both TLC and FEV1/FVC criteria.
- Ventilation/perfusion (V/Q) testing documenting absence of thromboembolic disease (normal or low probability V/Q scan)

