 - If no V/Q scan is available, a CT angiogram documenting the absence of thromboembolic disease may be used, provided the subject meets diagnostic PAH criteria (as above).

Exclusion Criteria

1. Age $<$ 18 years old
2. PAH associated with human immunodeficiency virus infection
3. Initiation of new background PAH therapy within 12 weeks of baseline visit
4. Significant dose change in background PAH therapy. The following ARE allowed:
 - a. within 12 weeks of baseline visit:
 - i. planned titration of prostacyclin analogue, selexipag, or riociguat $>$ 20%
 - ii. Plan to titrate to high dose sildenafil (e.g., 20mg to 80mg TID)
 - iii. Transition to prostacyclin analogues/selexipag (e.g., IV to oral, inhaled to IV)
 - iv. Increase in ambrisentan 5mg to 10mg or tadalafil 20mg to 40mg
 - b. within 4 weeks of baseline visit:
 - i. planned titration of prostacyclin analogue, selexipag, or riociguat $<$ 20%
 - ii. change from commercial to generic (or generic to commercial) ERA or PDE5i
 - iii. Interchange within drug class due to side effects (e.g., ERA to ERA, PE5i to PDE5i)
5. Untreated severe obstructive sleep apnea diagnosed by polysomnography
6. Evidence of left-sided valvular disease or systolic dysfunction on echocardiogram (\geq moderate mitral or aortic disease or LV ejection fraction \leq 50%)
7. Glomerular filtration rate $<$ 40 mls/min/1.73m²
8. Child-Pugh Class C cirrhosis
9. Untreated hypo- or hyper-thyroidism
10. Pregnant or breastfeeding
11. Active or planned use of hormonally active therapies with the exception of indwelling (>3months) levonorgestrel IUDs (see Appendix A for list of excluded medications and hormonal therapies).
12. History of breast, ovarian, uterine, testicular or prostate cancer
13. Current use of another investigational PAH therapy
14. Contraindication to MRI (e.g. metal device or fragment)
15. History of significant non-adherence or circumstance which would threaten ability to comply with cross-over design and study visit schedule

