C8.e. Subject recruitment and retention. The RIHPHC services a catchment area of all of Southern New England and is the only center accredited by the Pulmonary Hypertension Association as a Comprehensive Care Center in the region. The RIHPHC cares for >400 patients and offers comprehensive patient care services including diagnostic imaging, hemodynamic evaluation, a dedicated PH step-down unit, an interdisciplinary care team, and four full-time providers. The PI and staff of RIHPHC meet weekly to screen patients for enrollment in active research protocols. Eligible patients will be approached by their PAH clinician and then by the PI or research staff. Following screening and informed consent, a maximum of four weeks may lapse before randomization (baseline visit) and eligibility in order to confirm clinical stability. New or recent changes to PAH meds will be reassessed at the baseline visit. Serum pregnancy tests will be obtained at

baseline and at week 24 (after crossover) in premenopausal subjects. Retention and complete follow-up will be assured with frequent call reminders 3-5 days prior to study visits, 24/7 accessibility of research support staff, study drug adherence logs and pill counts, and monetary compensation and parking passes for study visits.

PAH in men is rare, however based on our trial enrollment over the past three years (n = 52, 25% men) and our recent study of men¹⁰¹ we anticipate recruiting 13 (50%) men during the study. Patient-level variation in end points as well as interactions by age, sex, race/ethnicity, and PAH sub-type will be assessed. We have met all of our enrollment targets for active studies, and consider this proposal a top priority for our center.

C8.f. Investigational therapy. We have already received an Investigational New Drug exemption (IND#129285) from the FDA for this study (see attached letter). We will purchase DHEA 50 mg daily tablets in a single batch from Green Mountain Pharmaceuticals (Lakewood, CO). Green Mountain is an Active Pharmaceutical Ingredient registered manufacturer with the FDA and has produced DHEA for ongoing trials at major centers including our institution (NCT01343771). Lots previously purchased

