from this manufacturer yielded >100% DHEA from an independent laboratory (FrontRangeLabs, Loveland, CO) (included with IND letter). We will also analyze and document purity in the batch purchased for this study. Study drug and placebo will be over-encapsulated by the Investigational Services Pharmacy (see letter of support). Dose, 18 week exposure and four week washout periods were chosen based on pharmacokinetics of DHEA, treatment duration required for RV changes, and early phase trial standards in endocrine and PAH.^{36, 110-113} Changes in RV function occur after just 12 weeks of PAH therapy, justifying the planned exposure period.³⁶

C8.g. Study protocol and burden. An 18 week supply of study drug will be dispensed following randomization at the baseline visit. Cardiac MRI for RV measures (Aim 1) will be assessed at baseline, week 18 and week 40, at the end of each period receiving active treatment or placebo. Laboratory (Aim1: NT-proBNP, galectin-3, RAGE, oxidative stress markers and those for safety; Aim 2: plasma NO-related markers and serum ET-1) and secondary end points will be assessed at baseline and all four study visits (Table 6). Data collection for history and physical exam, adherence, and adverse events will occur in the RIHPHC research room, followed by 6MWD in the RIHPHC hallway. Phlebotomy for study labs will be performed by trained personnel and cardiac MRI will be performed at the end of the visit in the MRI suite; labs and imaging will occur on the first floor of the same building where the RIHPHC is located. Subjects will complete the HRQOL measures on a tablet during downtime to reduce total visit time. We will offer a small meal after phlebotomy. Based on current protocols including similar tests we anticipate the total time for a study visit will be 90–120 min (visit #1, #3) and 210–240 min for visits with MRI (baseline, visit #2, #4).

C8.h. Drug and protocol adherence. Pill counts will be tracked at each visit. A phone call after visit #2 at week 18 will confirm plan for the washout period. A second call in the washout period prior to visit #3 will ensure start date for second course of study drug.

C8.i. Randomization and blinding. Randomization of drug sequence stratified by sex and PAH subtype (Period 1–Period 2; Period 2–Period 1) will be automated by a web-based program. Study personnel and

Table 6. Study protocol and end points

Timeline, week		2	18	19-22	24	40	42	Unscheduled
Study visit	Baseline	#1	#2	Washout	#3	#4		US

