Phone call		X	X				X	
Medical history	X							
Medications	X	X	X		X	X		X
History and physical exam	X	X	X		X	X		X
Laboratory/safety								
CBC, Chem 7, hepatic	X	X	X		X	X		as indicated
Hormone levels	X	X	X		X	X		as indicated
Insulin levels	X	X	X		X	X		as indicated
Cholesterol levels	X	X	X		X	X		as indicated
Triglyceride levels	X	X	X		X	X		as indicated
End points								
Aim 1: Cardiac MRI	X		X			X		
Aim 1: NT-proBNP, galectin-3, RAGE, redox	X	X	X		X	X		
Secondary: SF-36v2, emPHasis-10, FC, 6MWD	X	X	X		X	X		
Aim 2: NO-related markers	X	X	X		X	X		
Aim 2: ET-1	X	X	X		X	X		
Study procedures								
Dispense study drug	X							
Medication adherence		X	X		X	X		
Adverse events		X	X	X	X	X	X	X

subjects will be blinded to treatment order allocation. DHEA and placebo will have identical packaging, taste, and smell. Study drug will be dispensed at the start of each treatment phase (weeks 0–18 [Period 1]; 22–40 [Period 2]) with phone calls as outlined.

C8.j. Safety monitoring. The research coordinator ([name] RN, BSN) and research assistant will be available 24/7 by phone as needed for side effects and adverse events. An unscheduled study visit can also be performed if lab abnormalities on safety labs require retesting. Provisions for an unscheduled study visit can be found in Table 6. RIHPHC clinicians and research staff including the study PI will be capable of breaking the blind in case of an adverse event. A data safety monitoring board (DSMB) consisting of three independent clinician scientists with expertise in cardiology, pulmonology and/or endocrinology and a biostatistician with clinical trial experience will be assembled to review enrollment targets, protocol deviations, violations, and adverse events as described below. Conference calls will occur throughout the study period and on an as needed basis for serious adverse events. Please see Section C8.m.6. for specific safety end points and **Data and Safety Monitoring** document for further details.

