For subjects currently enrolled in EDIPHY, we may extend the active treatment period an additional four weeks (Total time of treatment = up to 22 weeks) to complete in person study visits and obtain end points which cannot be obtained virtually/by televisits (i.e., six minute walk distance, cardiac magnetic resonance imaging). This strategy optimizes subject safety (by moving the window out another four weeks, to avoid an in person study visit if conditions so dictate) while minimizing data loss, the chance of "wasted" participation, and our ability to detect efficacy which is best done with a subject on study drug. Based on a prior clinical trial of 381 subjects with systemic lupus erythematosus, which was conducted with a higher dose of DHEA for one year's duration with no serious adverse events (Petri et al., Arthr Rheum 2004), we believe this extension of only four weeks poses no additional risk to subjects.

The changes follow:

1. Continue study drug until 6MWT and cMRI can be completed (up to an additional 4 weeks); remainder of end points will be assessed virtually on their due date and then coincident with 6MWT and cMRI
2. Scheduling
 - a. Active subjects will be contacted proactively to inform them of any relevant updates to study conduct and address any concerns.
 - b. The consent addendum will be sent to their residence and reviewed by phone with a study staff member. If willing, study staff will ask the subject to send the completed form back. Study staff will then sign and send a copy of the consent to the subject.

Visit Procedures

1. Safety Labs and Laboratory Endpoints
 - a. If an off-campus laboratory is available to a subject, safety labs will be drawn and reviewed via remote medical record review.
 - b. Alternatively, if the subject has a previously scheduled clinical visit in the PH Center, safety labs and study labs will be ordered and drawn at this clinic visit.
2. 6MWT
 - a. If a subject has a previously scheduled clinical visit in the PH Center, a 6MWT will be performed at this visit.
 - b. Otherwise, study drug will be continued for up to 4 additional weeks until 6MWT can be obtained
3. cMRI
 - a. Study drug will be continued for up to 4 additional weeks until cMRI can be obtained

Other Study Drug Details

1. Study Drug Dispensing
 - a. Provisions for remote study drug dispensing are being discussed with Lifespan research pharmacy should any subject transition for Period 1 to Period 2.

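### The repeat pregnancy test at week 24 comes two weeks after Period 2 dosing starts, so a placebo-first woman who has conceived would begin DHEA before the planned test

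*Combined protocol and SAP*

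**What the plan says.** Section C8.e gives the pregnancy-testing rule: serum tests at "baseline and at week 24 (after crossover) in premenopausal subjects". No other test time appears in the document, and Table 6 has no row for it.

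The dosing calendar is in two places. C8.f says "Dose, 18 week exposure and four week washout periods were chosen" on pharmacokinetic and other grounds. C8.i says "Study drug will be dispensed at the start of each treatment phase (weeks 0–18 [Period 1]; 22–40 [Period 2", so the second course starts at week 22. Table 6 shows washout over weeks 19–22 and visit #3 at week 24, with no visit at week 22. For contact before the second course, C8.h describes a telephone call: "A second call in the washout period prior to visit #3 will ensure start date for second course of study drug".

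On pregnancy itself, Table 5 lists "Pregnant or breastfeeding" as exclusion 10. C8.d explains that one group of exclusions covers conditions in which DHEA "has uncertain or potentially harmful effects (#1, 9-11"), a range that includes criterion 10. The same section states: "We will include premenopausal women but will track menstrual cycle dates and measure sex hormones at each visit".

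Protocol Addendum 1 (COVID-19) adds: "we may extend the active treatment period an additional four weeks (Total time of treatment = up to 22 weeks"). It re-times the week 19, 21 and 42 telephone calls but does not mention the pregnancy test.

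**The concern.** The sections agree with one another on timing. The difficulty is the order of events: the retest follows the first Period 2 dose when it should precede it. In the placebo-first sequence that dose is the woman's first contact with DHEA, so a test before it could prevent all exposure of a pregnancy detectable by then. A test at week 24 can only stop exposure that has already begun. Her previous planned test was at baseline, 22 weeks before that dose.

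The protocol treats pregnancy as a reason not to give DHEA and evidently meant to recheck around the crossover. Week 24 appears to follow from the visit calendar: visit #3 falls two weeks into Period 2, just as visit #1 falls two weeks into Period 1. That spacing suits on-treatment safety laboratories but not an eligibility check.

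Women on DHEA first take placebo in Period 2, so this particular timing adds nothing to their DHEA exposure.

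**Working it through.** **Inputs.** Treatment period 18 weeks and washout 4 weeks (C8.f); Period 2 at weeks 22–40 (C8.i); repeat test at week 24 (C8.e); dose 50 mg daily (C8.a); 13 women planned, two sequences (C8.c); extension of up to 4 weeks (Addendum 1).

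**Reproducing the plan's calendar.** Period 2 start = 18 + 4 = week 22. Period 2 length = 40 − 22 = 18 weeks. Both agree with C8.i and C8.f.

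**Exposure before the planned test, placebo-first sequence.**
- Time on drug = 24 − 22 = 2 weeks = 14 days.
- DHEA taken = 14 × 50 mg = 700 mg.
- Share of Period 2 = 14 / (18 × 7) = 14 / 126 = 11.1%.

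**Alternative reading of Table 6.** If washout lasts to the end of week 22, dosing starts at week 23 and the gap is (24 − 23) × 7 = 7 days. That conflicts with the stated 22–40 window and the 18-week exposure, and the test still follows the dose.

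**Women affected.** Number = 13 × 0.5 × premenopausal share. Equal allocation and the share are assumptions; the documents give neither.

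| Premenopausal share | Placebo-first premenopausal women |
|---|---|
| 0% | 0 |
| 25% | 13 × 0.5 × 0.25 = 1.6 |
| 75% | 13 × 0.5 × 0.75 = 4.9 |
| 100% | 6.5, i.e. 6 or 7 |

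These are women exposed to the gap, not expected pregnancies. The documents give no basis for a conception rate.

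**COVID-19 extension.** With the full four weeks added to Period 1, it ends at week 22 and Period 2 starts at 22 + 4 = week 26. A test held literally at week 24 then falls 2 weeks before dosing. A test kept with visit #3 moves to 26 + 2 = week 28, which is 2 weeks after dosing. The addendum does not say which applies.

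**After the change.** A test at the Period 2 hand-off (week 22) leaves 0 days of drug before the test. A test on the existing week 18 draw comes 22 − 18 = 4 weeks = 28 days before the dose, so it leaves the washout uncovered.

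**The case against.** The strongest reply is that the trial does not leave these women unobserved. Menstrual dates are tracked. There is an in-person visit at week 18 with examination, hormone levels and safety laboratories, adverse events are asked about in washout, and staff can be reached at any hour. A pregnancy conceived early in Period 1 would probably be noticed. The realistic case is conception late in Period 1 or during washout, in a handful of women at most. The documents show no evidence of harm from 14 days at 50 mg beyond the general caution in C8.d. All of this is fair and limits the size of the risk. None of it is a pregnancy test before dosing, and no test is tied to a missed period.

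It can also be said that larger untested intervals exist. A DHEA-first woman has no planned test between baseline and week 24, so all 18 weeks of her active course pass without one. A placebo-first woman has none from week 24 to week 40. That is true, but it is a separate weakness and does not justify placing the one planned retest after the dose.

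A test at week 22 could miss a very recent conception that week 24 would catch. This stands, and it is a reason to keep the later test as well.

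Finally, the protocol refers to a separate Data and Safety Monitoring document, a detailed monitoring plan for the IRB and a Human Subjects Protection document, which are not part of the public text. A pre-dose test may be required there. That cannot be excluded, but C8.e states the testing schedule without pointing to any such requirement.

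**Conclusion.** The concern holds. Under C8.e, C8.f and C8.i as written, the repeat pregnancy test follows the first Period 2 dose by 14 days. A placebo-first premenopausal woman who has conceived could take 700 mg of DHEA before the planned test. The 14 days assume that dosing starts at week 22 as C8.i states and is taken daily. The count of 0 to 7 women assumes equal allocation to the sequences and an unknown premenopausal share.

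The probability of an event is low, and the trial's statistical conclusions are unaffected. The change is still worth making, because the exposure is avoidable, the protocol itself regards pregnancy as a reason to withhold the drug, and the remedy is cheap.

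**What to change.** In C8.e, require a negative pregnancy test before the first Period 2 dose in every premenopausal subject. Define the timing by that dose and not by a calendar week, so that the rule also holds when Period 1 is extended under the COVID-19 addenda. The natural moment is Period 2 dispensing, at about week 22. Keep the week 24 test to pick up very recent conceptions.

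If a draw near week 22 is not practicable, the minimum is to add the test to the existing week 18 blood draw and keep week 24, accepting that conceptions during washout are then not covered before dosing.

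Add a pregnancy-test row and a Period 2 dispensing mark to Table 6, so that it matches C8.e and C8.i. If another trial document already requires a pre-dose test, C8.e should say so.

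The cost is one sentence in C8.e and two entries in Table 6, plus one extra blood test. Week 22 is not a scheduled visit, so the preferred option needs a draw at the drug hand-off; the week 18 option needs no new draw.
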